intervention fidelity; and maximize participant retention. Detailed records on recruitment, session attendance, and homework completion will be kept throughout the intervention. Consistent with Consolidated Standards of Reporting Trials (CONSORT) guidelines, we will obtain data to determine (1) the number of participants who reported moderate or greater symptom ratings, or who have impairments in one or more cognitive domain, from the baseline assessment; (2) the number of participants referred to the study, (3) the number of participants screened by research staff for study eligibility, and (4) the number enrolled in and completing all aspects of the study including treatment sessions and assessments. We will ascertain reasons for unsuccessful recruitment, ineligibility, and unsuccessful enrollment of eligible Veterans. In addition, we will collect data on the intensity of outreach needed to recruit and enroll participants (e.g., number of phone calls required before Veterans complete eligibility screening, number of "no shows" for eligibility screening appointments) and length of time between initial recruitment attempt, eligibility screening, and completion of the pre-intervention assessment. Participant Retention will be measured by the proportion of participants who complete follow-up assessments within two weeks of the target date. Treatment satisfaction will be assessed by the Client Satisfaction Questionnaire (CSQ8).

Functional and Clinical Variables: We will use similar assessment procedures as in the Aim 1 study to assess cognitive and functional domains most strongly associated with PTSD (details listed in the table below). We will examine sleep and mental health symptoms (including PTSD and depression) not directly targeted by CCT to examine comparability to TAU. Assessments will take approximately 1.5 hours and will occur at baseline, post-treatment, and 6-month follow-up for both groups.

Measure	Construct Assessed			
Objective Cognitive Functioning (Neuropsychological Tests)				
Test of Premorbid Functioning (ToPF)	Verbal abilities; estimate of premorbid cognitive functioning			
California Verbal Learning Test (CVLT-II; Delis et al., 2000)	Verbal learning and memory, forced choice validity			
Wechsler Adult Intelligence Scale (WAIS-IV) Digit Span & Coding subtests (Wechsler, 2008)	Attention, working memory, processing speed, reliable digit span validity			

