Randomization and Blinding: All eligible participants will be randomized to either the CCT or TAU group. Randomization tables will be prepared by the study statistician at the beginning of the study and assignments to CCT or TAU will be based on the randomization table. New participants will be allocated to the current group awaiting randomization. Once group membership reaches 6 participants, the group will be randomized by the statistician. We will employ a system of adaptive randomization, weighted to achieve the desired proportion of participants in each condition, managed by the statistician. Randomization will be implemented by the study coordinator in coordination with the statistician who will monitor randomization procedures. Because of the small sample size and number of study personnel in this pilot RCT, it might not be feasible to blind the assessor to participant group status if the assessor is also co-facilitating CCT groups with [name], though this type of blinding will be implemented if possible.

Data Analysis: Rates of recruitment, retention, and participation will be calculated, and we will compare participant characteristics at baseline by group (CCT vs. TAU). We will conduct intent-to-treat analyses to compare change from baseline to 3-month follow-up within and between groups.

Study Feasibility Analyses: Descriptive statistics will characterize the feasibility of recruiting and retaining Veterans. Recruitment will be deemed feasible if we successfully screen for eligibility 50% of Veterans referred to the study and enroll 75% of screened Veterans who meet all study inclusion criteria. Retention will be deemed successful if we achieve 80% completion for post-treatment assessments. Chi-square tests of association for categorical variables and t-tests for continuous variables will compare demographic and clinical characteristics of successfully versus unsuccessfully recruited and retained Veterans to identify characteristics of participants who may require more intensive recruitment or retention efforts in a future trial.

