Enrollment and Assessment Procedures: Prior to enrollment, interested Veterans will be prescreened. The study coordinator will conduct a medical record review to document cognitive symptoms, medical and psychiatric history, and recent treatments and medications. The Neurobehavioral Symptom Inventory (NSI) will be used as a screening tool to determine the presence of moderate or greater cognitive symptoms for eligibility purposes. A brief phone interview will ensure that Veterans are interested in participating and meet eligibility criteria. All participants will be screened to ensure their ability to comprehend study procedures, risks and benefits. We anticipate that up to 500 Veterans will need to be screened in order to achieve the desired sample size of 36-48 Veteran participants in the study. Veterans will be provided the opportunity to have the informed consent materials mailed to them. After the Veteran receives the informed consent materials, a trained study team member will call the Veteran to go through the informed consent procedures and answer any questions. If the Veteran chooses to participate, he or she will sign the informed consent documents and mail them back to [name] using a pre-addressed and stamped envelope. The study assessment will only be scheduled after the hard copy informed consent is received back from the Veteran. Following determination of eligibility, provision of informed consent, and enrollment into the pilot trial, Veterans will initiate the pilot RCT assessments, and, when assigned to the CCT condition, the 10-week CCT group intervention (weeks 2-11). Cognitive assessments and symptom questionnaires will be completed at baseline, post-treatment (approximately 3-months following baseline), and follow-up (6-months following baseline). Veterans will have the option to complete all study activities, including the 10-week CCT intervention and the 3 cognitive assessments via the VA's telehealth system, VA Video Connect (VVC), or via telephone.

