health clinics. With approval of the clinical providers, additional eligibility screening will take place for up to 120 Veterans; the Veterans who meet eligibility criteria will be contacted until the desired sample size of 36-48 participants are enrolled in the study. There is currently a waiver of informed consent to be able to review Veterans' medical records to ensure medical inclusion and exclusion criteria are met prior to contacting potentially eligible Veterans. This may reduce time and travel burden for Veterans who do not meet these minimum study criteria. [name] or another study member will let VA mental health clinicians know about the study and inclusion/exclusion criteria and request their assistance in recruiting eligible Veterans. This information will be provided to clinicians in the form of an email, in person conversation, team meeting presentation, or phone call using the attached email letter/script. Veterans meeting these study criteria will be informed of the study by their clinician from the mental health clinic in which they receive mental health treatment. If they are willing to participate, the clinician will notify [name] through CPRS, encrypted email, or in person meeting, or phone call that the Veteran agreed to be contacted about the study. Veterans who express interest in participating will be called to schedule a meeting to discuss and obtain informed consent and to conduct the 90-minute baseline assessment and be randomized to CCT or TAU group if they consent to study participation. During the initial scheduling call, Veterans will be given the option to conduct the baseline visit (i.e., discuss and obtain informed consent and conduct the 90-minute baseline assessment) in person, via VVC, or via telephone; staff will follow current VA guidance about inperson visits and will allow for participant preference when permitted by the VA (e.g., if the Portland VA does not recommend in-person for non-essential visits, then this option will not be offered, and only VVC or telephone appointments will be offered).

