If the Veteran chooses to conduct the meeting via telephone or VVC, the study team will schedule a telephone or VVC appointment to go over study documents (i.e., Informed Consent Form and HIPAA Authorization) using DocuSign. An approved study team member will send a DocuSign envelope (an email containing links to the study documents) to the potential participant. The email will contain a reminder for the Veteran to not sign the documents prior to the scheduled contact time, when study staff will review the documents with the Veteran and answer any questions. At the scheduled appointment, approved study staff will contact the potential participant via phone or VVC and use the e-consenting script to walk the Veteran through the DocuSign process, including opening and reviewing the documents. For reference, staff will have opened a copy of the documents on his/her own computer. If the Veteran agrees to be in the study, staff will direct the Veteran to fill in any required fields and sign the document. Once the Veteran has signed the documents, the Veteran will click "Finish" to finalize the documents. While still in the appointment with the Veteran, study staff will verify that the signed documents have been completed accurately and completely as well as signed. Study staff will sign the documents and then direct the Veteran on how to save a copy for his/her own records. After the appointment, study staff will print a copy of the signed documents to be delivered for review to the privacy officer, following the same procedure as in-person visits. The study staff will document the consenting process in CPRS.

If the Veteran chooses to conduct study activities in person and this modality is allowed by the Portland VA at the time, the Veteran will be scheduled for an in-person meeting to discuss and obtain informed consent and to conduct the 90-minute baseline assessment. At all stages of eligibility determination and study involvement, all Veteran participants will be provided an opportunity to have their questions answered.

12

Risks and Side Effects:

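### Visits are dated from each Veteran's baseline, but CCT waits for a group of six, so the post-treatment visit can fall before CCT is finished and, if accrual is slow, before it begins

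*Combined protocol and SAP*

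**What the plan says.** Four parts of the protocol bear on timing.

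- **Enrollment and Assessment Procedures** dates the later visits from baseline: "post-treatment (approximately 3-months following baseline), and follow-up (6-months following baseline". It places "the 10-week CCT group intervention (weeks 2-11" on that same clock. For mailed consent it says "The study assessment will only be scheduled after the hard copy informed consent is received back from the Veteran", which sets an earliest moment for baseline but does not tie it to the group being full.
- **Randomization and Blinding** puts each new participant into a group awaiting assignment: "Once group membership reaches 6 participants, the group will be randomized by the statistician".
- **Informed Consent & HIPAA Authorization** joins consent and baseline in one contact. Interested Veterans are called to a meeting "to conduct the 90-minute baseline assessment and be randomized to CCT or TAU group if they consent to study participation". For attendance in person, "the Veteran will be scheduled for an in-person meeting to discuss and obtain informed consent and to conduct the 90-minute baseline assessment".
- **Data Analysis** names the contrast: "compare change from baseline to 3-month follow-up within and between groups".

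Feasibility and Acceptability counts a Veteran as retained if the follow-up assessment is done no more than two weeks from its due date. It also records "length of time between initial recruitment attempt, eligibility screening, and completion of the pre-intervention assessment". That interval stops at baseline, so the wait from baseline to assignment is not among the listed data.

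**The concern.** Five of every six members of a group wait after baseline for others to join. The stated CCT weeks are right only for a Veteran who hardly waits. Randomising at the baseline contact, as the consent section implies, is not possible for a member of a group that is still filling.

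The text leaves staff two courses, and each causes a problem.

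- **Visit held at 3 months from baseline, as written.** Early joiners in the CCT arm are scored part-treated or untreated. The intent-to-treat analysis rightly keeps them, so if CCT works, the estimated effect is pulled toward zero. Aim 2 exists to supply that estimate for the next trial's sample size.
- **Visit held until CCT ends.** It is then late under the retention measure if the due date is counted from baseline, and the baseline-to-outcome interval depends on the order of joining. Unless TAU visits move by the same amount, the arms are also compared at different intervals.

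**Working it through.** **Inputs from the protocol.** Ten weekly sessions; CCT in weeks 2-11; visits at about 3 and 6 months from baseline (13.0 and 26.1 weeks); groups of six; 36 to 48 Veterans; a two-week retention window.

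**Assumed inputs.** Accrual rate, because none is stated. Filling 36-48 places takes 3-4 Veterans per month over 12 months (36/12, 48/12), 1.5-2 over 24 months and 1-1.3 over 36 months; 8 per month is added as a fast case. The first session is taken as 1 week after the group fills, with 0 and 2 weeks also run.

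**Step 1: the plan's own schedule.** With no wait, CCT starts 1 week after baseline and ends by week 11. The visit falls at about week 13, so the schedule fits with about 2 weeks to spare.

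**Step 2: add a wait of W weeks.** The first session is at W + 1 and the tenth at W + 10.
- Finished by week 13 if W + 10 ≤ 13, so W ≤ 3 weeks (W ≤ 5 if the visit is two weeks late).
- Not begun at week 13 if W + 1 > 13, so W > 12 weeks.
- Counting CCT to the end of its last week instead of to the tenth session cuts the tolerated wait to about 2 weeks (13.0 − 11).

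**Step 3: rate needed for the first joiner.** With evenly spaced arrivals, five more must enrol in 3 weeks: 5/3 × 4.35 = 7.25 per month. The whole pilot would then fill in 36/7.25 = 5.0 to 48/7.25 = 6.6 months. On the stricter 2-week count the rate is about 10.6 per month. The first joiner has not begun CCT at week 13 if accrual is below 5/12 × 4.35 = 1.8 per month.

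**Step 4: share of CCT members affected.** Arrivals are taken as random (Poisson) at λ = rate/4.35 per week. A member who joins with k still to come (k = 0 to 5) waits a gamma time with shape k, so

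P(W > t) = Σ e^(−λt)(λt)^i / i!, for i = 0 to k − 1,

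averaged over the six positions. Example at 2 per month: λ = 0.46, t = 3, λt = 1.38. For k = 0 to 5 the probabilities are 0, 0.252, 0.599, 0.838, 0.949 and 0.987, which sum to 3.625; 3.625/6 = 60%.

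| Veterans per month | 1 | 2 | 3 | 4 | 8 |
|---|---|---|---|---|---|
| Unfinished, week 13 | 72% | 60% | 49% | 39% | 11% |
| – start lag 0 to 2 weeks | 68-76% | 53-68% | 39-60% | 27-53% | 4-27% |
| Unfinished, week 15 | 64% | 46% | 30% | 18% | 1% |
| Unfinished, week 26 | 27% | 4% | 0.3% | 0% | 0% |
| Not begun, week 13 | 39% | 11% | 2% | 0.3% | 0% |
| Mean sessions delivered, week 13 | 4.5 | 6.8 | 8.1 | 8.9 | 9.8 |
| Mean sessions delivered, week 15 | 5.2 | 7.75 | 9.0 | 9.6 | 10.0 |
| First joiner's mean wait, weeks | 22 | 11 | 7 | 5 | 3 |

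The 2-week lag gives nearly the same result as the stricter count in step 2.

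**Step 5: illustration for Aim 2.** Suppose benefit were proportional to sessions delivered, which the protocol does not claim. The week-13 effect at 2, 3 and 4 per month would be about 68%, 81% and 89% of full. Required sample size varies as 1/(effect)², so it would come out 1/0.68² = 2.2, 1/0.81² = 1.5 and 1/0.89² = 1.3 times too large. With the visit at week 15 the multiples are about 1.7, 1.2 and 1.1.

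**The case against.** The strongest reply is that nobody would score a Veteran as post-treatment before treatment. The visit carries that name throughout, the 3 months is only approximate, and CCT in weeks 2-11 makes sense only if baseline falls just before the group starts. The consent section does not say when, relative to the group filling, the consent-and-baseline meeting is booked. On this reading the plan lacks a stated anchor but does not have a failing schedule.

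Part of this stands. Staff may well have meant to wait, and the not-begun case is material only at slow accrual: 2% or less at 3 or more per month. But no section delays baseline or moves the visit, and waiting brings the second problem described above. An approximate 3 months cannot plausibly absorb a first-joiner wait that averages 11 weeks at 2 per month, and the 6-month visit carries no such qualifier.

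Other mitigations are real but partial. The outcome models use change over time and include a 6-month visit, by which few are unfinished at 2 or more per month. Number of sessions attended is a planned moderator. Effect sizes will be compared with those from the mild TBI trial. The pilot is also imprecise: with 24 v 12 or 30 v 18 Veterans, the 95% half-width on a standardised difference is about 1.96 × √(1/24 + 1/12) = 0.69 or 1.96 × √(1/30 + 1/18) = 0.58, so dilution of 10-20% in a moderate effect is small beside the noise. It is bias, though, and a future sample size would inherit it. None of these points sets the visit anchor.

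**Conclusion.** The concern holds. The sections on randomisation, consent and assessment timing do not fit together. Followed as written, they can place part-treated CCT members in the baseline-to-3-month contrast.

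The contradiction does not depend on the accrual rate; its size does. Over the assumed 1 to 8 Veterans per month, the share unfinished at week 13 runs from 72% to 11%. At the 2-4 per month that would fill 48 places in 12 to 24 months, it is about 40-60% at week 13 and 18-46% at week 15. These figures assume random arrivals, a 1-week start lag and visits held on the baseline clock. The sample-size multiples are illustration only. The point should be fixed, with medium confidence in its size because neither accrual nor actual practice is documented.

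**What to change.** Reconcile Randomization and Blinding, Enrollment and Assessment Procedures, and Informed Consent & HIPAA Authorization around one time origin.

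1. Define week 0, for both arms, as the date the group of six is randomised.
2. Consent and screen Veterans as they come, but give the baseline battery shortly before week 0, once the sixth member has consented. State what happens if a member withdraws between consent and baseline.
3. Count the post-treatment and 6-month due dates, and the two-week window, from week 0 for CCT and TAU alike.
4. For groups already enrolled, record the wait from baseline to randomisation and use actual time since group randomisation in the multilevel model.
5. Add a sensitivity analysis that leaves out, in both arms, visits made before the date of the group's tenth week.

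The cost is mostly wording. Consent and baseline become separate contacts for early joiners, and some may be lost while they wait (see the last row of the table). Those losses come before randomisation, so they do not bias the CCT-TAU comparison, but they should be counted in the Aim 1 recruitment results. Enrolment status at this version (January 2024) is not stated. If few groups remain to be formed, items 4 and 5 do most of the work.

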In this pilot study, we will first examine descriptive statistics, and conduct tests of normality and homogeneity of variance for variables included in repeated measures analyses. We will examine missing data for all variables and dropout rates in order to plan for a future RCT. though will not conduct multiple imputation or other missing data techniques for this pilot study. We will, however, conduct intent to treat analyses, analyzing data from all randomized participants assigned to CCT versus TAU groups, rather than only including completers. Primary outcome analyses will be multilevel models to compare the change over time in cognitive, mental health, functioning, and QOL outcomes for Veterans in the CCT versus TAU groups. If the sample size is too small to run multilevel models, we will run alternative methods such ANOVAs which are more feasible with smaller samples. We will examine how much symptoms change, comparing changes across groups, and also examine clinically significant change in self-reported functional and clinical outcomes. We will compare the change in proportions of Veterans who fall within in "clinically significant impairment" ranges on objective cognitive performance measures before and after CCT versus TAU, characterizing cognitive functioning deficits according to cognitive domains. Because of the small sample size in this pilot RCT, these analyses will rely heavily on descriptive statistics including identifying individuals who score within clinically impaired ranges on objective testing, and who score above clinical cutoffs on self-report measures. Multilevel models or repeated measures analysis of covariance (ANCOVA) models will examine potential moderators including validity tests, service connection status and percent, number of sessions attended, comorbid mental health diagnosis such as PTSD, and demographic variables.

Study Population and Subject Identification/Recruitment

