If a Veteran chooses to complete intervention activities via VVC or telephone, a study team member will mail the Veteran the CCT session materials. If a Veteran chooses to complete the intervention activities via VVC, [name] or another trained, IRB-approved study team member will explain how VVC works and ensure that the Veteran has the appropriate technology and accommodations to ensure VVC will work (i.e., internet connected device with video chat capabilities, internet connection, private space to engage in the intervention). A study team member will schedule intervention sessions with the Veteran and then the Veteran a link for VVC through Virtual Care Manager. If a Veteran chooses to complete intervention activities via VVC or telephone, [name] or another trained, IRB-approved study team member will conduct the intervention via VVC or telephone. If a Veteran chooses to complete assessments via VVC or telephone, a study team member will administer all cognitive tests over the phone by reading the instructions and questions to the Veteran and recording their response. All responses will be recorded directly into electronic files maintained in the IRB-approved VA folders behind the VA firewall. No hard copy or other electronic files will have any study data. All assessment activities can be completed via VVC or telephone with the exception of the Halstead Reitan Trailmaking Test parts A and B and the Wechsler Adult Intelligence Scale Coding subtest. If a Veteran chooses to complete an assessment via VVC or telephone these tests will not be administered.

Participant retention/ Dropout Minimization: Retention activities will include offering the option to complete study activities via VVC or telephone, inviting participants who discontinue treatment

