to complete follow-up assessments, advance participant reminders of upcoming assessments, scheduling assessments near the target date at times that are convenient for participants, providing reminder calls 1-3 days prior to the scheduled assessment, and promptly rescheduling missed assessment appointments. We will attempt to retain all enrolled Veterans in the study, regardless of ongoing participation in CCT or other interventions as part of TAU. In our prior research, all Veterans who initiated CCT completed the intervention. For Veterans who discontinue treatment and who express discomfort returning to the clinic to complete follow-up assessments, accommodations will be made to ensure Veterans have the opportunity to continue study participation (e.g., assessment completion via VVC or telephone or at other VAPORHCS locations). We will ensure that participants are appropriately reimbursed for time and travel, paying participants \$50 for each assessment. Recent trials of CCT in VA clinics conducted by Drs. [name], [name], and [name] have exceeded 90% retention.

Inclusion/Exclusion Criteria

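### A change of assessment mode changes the tests behind executive functioning and processing speed, so before/after impairment by domain can move with no true change

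*Combined protocol and SAP*

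**What the plan says.** **Tests by mode.** Under Enrollment and Assessment Procedures, "All assessment activities can be completed via VVC or telephone with the exception of the Halstead Reitan Trailmaking Test parts A and B" and the WAIS-IV Coding subtest. It continues: "If a Veteran chooses to complete an assessment via VVC or telephone these tests will not be administered". No substitute test is named.

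**Choice of mode.** The same section offers telehealth or telephone for all three cognitive assessments. Informed Consent & HIPAA Authorization adds that the in-person option is withheld when site guidance advises against non-essential visits. For Veterans who stop treatment and are uncomfortable returning to the clinic, Participant retention/Dropout Minimization offers accommodations, for example "assessment completion via VVC or telephone or at other VAPORHCS locations". No section keeps a Veteran in one mode.

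**Analysis.** Clinical and Functional Outcome Analyses states: "We will compare the change in proportions of Veterans who fall within in" the clinically impaired range on objective tests "before and after CCT versus TAU, characterizing cognitive functioning deficits according to cognitive domains". All randomized Veterans are included and no missing-data technique is used. The primary analyses are multilevel models of change over time. Separately, Feasibility and Acceptability counts, at baseline only, Veterans with moderate or greater symptom ratings or with "impairments in one or more cognitive domain, from the baseline assessment".

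**Not stated.** The plan gives no impairment cut-off and no list of the tests that make up a domain. It has no rule for a domain whose tests were omitted and none for handling mode in the analysis.

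**The concern.** A before/after comparison of impairment status needs the same yardstick at both visits. Here the yardstick depends on how the visit was held. A Veteran tested in person once and remotely once has executive functioning judged on two different sets of tests. Processing speed is judged at one visit and not at the other. Impairment status can then change although performance has not.

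The plan says its impairment analyses will lean heavily on descriptive statistics, including identifying individuals in impaired ranges, and Aim 2 carries effect estimates into the design of a larger trial. A shift produced by mode could be read as a treatment effect, or could hide one. The baseline any-domain count is exposed in a simpler way: fewer tests give fewer chances of being counted.

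**Working it through.** The plan gives no impairment rate, cut-off or power figure on this point, so there is no figure of its own to reproduce. The check has three steps.

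**1. Tests available by mode** (measures table under Functional and Clinical Variables, set against the remote-testing rule). Coding is read here as the processing-speed part of its shared table row with Digit Span.

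| Domain | In person | Remote |
|---|---|---|
| Verbal learning/memory | CVLT-II | CVLT-II |
| Attention/working memory | Digit Span | Digit Span |
| Executive functioning | Trails, COWAT | COWAT |
| Processing speed | Coding, Trails | none |

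Only the last two rows depend on mode. Processing speed becomes missing. Executive functioning stays scorable, but on a different set of tests.

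**2. Size with no true change.** This is a simulation of 1,000,000 people with one normal score, SD 1, for each of six tests.
- Means are either 0 or the PTSD deficits quoted in Scientific Rationale and Significance: verbal learning -0.62, attention/working memory -0.50, executive -0.45 (COWAT, Trails B), speed -0.59 (Coding, Trails A).
- Assumed, not in the documents: use of those deficits as shifts from test norms, allocation of Trails A to speed and Trails B to executive functioning, equal correlation r of 0.3, 0.5 or 0.7, and a cut-off of -1, -1.5 or -2 SD.

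Executive functioning at r = 0.5, cut-off -1.5 and the quoted deficits:
- COWAT alone: Φ(-1.5 + 0.45) = Φ(-1.05) = 14.7%.
- Any-test rule, COWAT or Trails B: 23.8%. A switch from in person to remote gives 14.7 - 23.8 = **-9.1 points**, an apparent improvement.
- Mean-of-tests rule: the SD of the mean is √((1 + 0.5)/2) = 0.866, so Φ(-1.05/0.866) = Φ(-1.21), about 11%; the simulation gives 11.2%. The same switch gives 14.7 - 11.2 = **+3.5 points**, an apparent worsening.
- Across all scenarios the any-test fall is 1.6 to 16.9 points and the mean-of-tests rise is 0.8 to 5.1 points. A switch from remote to in person reverses each sign.

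Processing speed, same setting, any-test rule: 28.7% in person. At a remote visit it is missing, or a spurious 0% if an untested domain were counted as unimpaired.

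Baseline count of at least one impaired domain, same setting, any-test rule: 46.5% in person against 33.3% remote, a difference of 13.2 points (2.6 to 17.4 over all scenarios).

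**3. From the Veteran to the arm.** The artefact in an arm is the shift per switcher times the net share switching from in person to remote; between arms it is the shift times the difference in those shares. The shares below are assumed.
- 20% in both arms, any-test rule: -9.1 × 0.20 = -1.8 points in each arm, and 0 between arms.
- 50% against 10%: 9.1 × 0.40 = 3.6 points between arms under the any-test rule, and 3.5 × 0.40 = 1.4 points in the opposite direction under the mean-of-tests rule.

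**The case against.** The strongest reply is that little of the planned analysis is touched. Verbal learning/memory and attention/working memory keep their tests. Multilevel models fitted test by test lose Trails and Coding observations at remote visits, but they never compare one test set with another. Processing speed is simply missing unless an untested domain is scored as unimpaired, which the plan does not say. This is a pilot, and power is expressly not a primary concern. With 24-30 CCT and 12-18 TAU Veterans and proportions near 50%, the standard error of a between-arm difference is about 15 to 18 points: √(0.25/30 + 0.25/18) = 0.149 and √(0.25/24 + 0.25/12) = 0.177. An artefact of 3.6 points is small beside that. All of this stands, and it limits the point to the domain-level impairment summaries.

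Three stronger readings are tempting, and the documents support none of them.
- A reader might infer that going remote makes Veterans look improved. That holds under an any-test rule and a switch from in person to remote; a mean-of-tests rule or the opposite switch reverses it.
- A reader might take the any-domain difference of about 13 points as bias in a before/after outcome. The any-domain count is planned at baseline only. It is also joined by an or to symptom ratings; if those are the NSI ratings required for entry, the combined count is near 100% in either mode.
- A reader might infer that the CCT-TAU comparison is biased. Remote testing is one example of an accommodation for Veterans who both stop treatment and are uncomfortable returning. The same section reports that all Veterans who began CCT in prior research completed it, with retention above 90% in recent trials. Differential switching is possible, but no figure for it is given.

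What survives is that executive functioning changes its test set while remaining scorable, and that nothing says how an untested domain is to be handled.

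**Conclusion.** The point holds as a cheap improvement, not as a flaw in the primary analysis. When a Veteran's mode changes between visits, executive-functioning impairment is measured with different tests and processing speed cannot be measured at the remote visit, so before/after impairment by domain can shift without true change.

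For executive functioning the shift per switcher is a fall of 1.6 to 16.9 points (any-test rule) or a rise of 0.8 to 5.1 points (mean-of-tests rule) when going from in person to remote. These sizes rest on the assumed correlations, cut-offs, means and test allocation. The effect on an arm scales with the share who switch. The between-arm effect is zero if net switching is equal, and it cannot be sized from the documents. The any-domain part of the baseline count depends on baseline mode in any case.

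**What to change.** Before the data are examined:
1. List the tests that make up each domain, with the cut-off and the rule (any test, or mean of tests).
2. For each Veteran, score before/after impairment change only on tests given at both visits being compared. Treat processing speed as not evaluable, rather than unimpaired, when either visit was remote. This removes the omission artefact by construction.
3. Keep each Veteran in the same mode across visits unless that would lose the visit.
4. Record mode at every assessment, tabulate it by arm and visit, and report the baseline any-domain count by mode.

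Do not add follow-up mode as a covariate in the treatment-effect models. It arises after randomization and may depend on arm, and its effect cannot be estimated for Trails or Coding, which exist only in person. Nor is there a need to drop processing speed for everyone: matching tests within each Veteran keeps it wherever both visits were in person.

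The cost is some wording and one recorded variable. The downside is that fewer Veterans are evaluable for processing speed, and executive functioning rests on COWAT alone for anyone with a remote visit in the comparison. The evaluable subset is selected partly after randomization, so its results should be labelled descriptive. Remote assessment stays available, with its benefit for retention.
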